2.1 Primary Objective

This pilot study will provide feasibility on use of wearable technology for tracking and selfmonitoring PA as well as preliminary data to support our overall approach for promoting PA and improving disease status in a Hispanic women population. A larger application will be submitted to the NIH, DoD, or other federal agency focused on investigating the impact of PA on chronic neurological diseases in a diverse and inclusive Hispanic population in LA County.

2.1.1 Specific Aim 1

Specific Aim 1 establishes feasibility of this approach by measuring adherence and change in PA using a Fitbit Alta HR activity monitor in Hispanic women with chronic neurological diseases. Adherence will be determined through: (i) the average hours/day of use; and (ii) the length of time (percent of total study days) of usage throughout the 16-week study. Adherence defined as (i) 5 or more days/week of use and (ii) 10 or more hours of use during the day.

2.1.2 Specific Aim 2

Specific Aim 2 tests the hypothesis that an increase in physical activity will be correlated with a decrease in LA County (LAC) Facilities health care use (hospital and clinic visits). Physical activity will be assessed by change in either: (i) the average number of steps/week; and (ii) average time spent in sedentary, light, or moderate to vigorous intensity based on MET (metabolic expenditure) of physical activity/week. Methods: Changes in PA outcome metrics over the 16-week period will be correlated with the total number of hospital/outpatient clinic visits. Total hospital use will be determined through the LAC/DHS (Department of Human Services) electronic medical records and will include outpatient provider visits, emergency room and urgent care visits, total hospitalizations, and days spent in hospital.

2.1.3 Specific Aim 3

Specific Aim 3a tests the hypothesis that increase in physical activity is associated with an increase in the quality of life (QOL). Physical activity will be measured through: (i) the average number of steps/week; and (ii) average intensity of physical activity/week. QOL will be determined through measures of self-rated health and well-being. These Spanish validated surveys will include illness perception questionnaire and health and well-being questionnaire

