3.0 STUDY DESIGN

3.1 Overall Study Design

This is a 16-week single group study of PA promotion and monitoring along with its effect

on Neurological Health. Twenty Hispanic women seen at LAC/USC Neurology clinic will be referred to TWC and invited to participate in a physical activity (PA) study for 16 weeks. Participants will receive individualized Fitbit Charge activity monitors at baseline and instructed on its usage and maintenance. Adherence to activity monitor use and amount and level of PA will be determined. All assessments that include quality of life, exercise behaviors, and self-rated health and mood will be made at baseline and at 16 weeks at TWC. Educational/coaching will take place through (i) individualized instruction on exercise at baseline and at the end of week 4 at TWC and (ii) weekly calls from TWC to promote PA goal setting as well as Fitbit use. At the end of week 1, participants will be asked to return to the TWC to review instructions on Fitbit App use and to receive further education on the benefits of exercise through a brief Power Point presentation. Patient may also receive text messages throughout the study to remind them of upcoming appointments or deadlines. General Neurological Health status will be determined through use of Electronic medical records to determine hospital and outpatient clinic visits through the 16 weeks. At study completion, participants will be allowed to keep their Fitbit activity monitor and will receive a 3-month follow up post-study call to assess the continued usage of the Fitbit charge activity monitor and a quality of life questionnaire.

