3.2 Enrollment Plan

Twenty (20) Hispanic women with a chronic neurological disorder will be recruited from our LAC/USC Neurology Clinic. We expect to achieve this goal by 2 months from study start.

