8.0 STATISTICAL CONSIDERATIONS

8.1 Statistical Methods

Preliminary analyses will begin with an examination of the distribution of key variables to assess their characteristics (means, standard deviations, skewness, and kurtosis), to provide descriptive statistics of the study population. Continuous measures will be tested for normality and homogeneity of variance. Non-normally distributed variables will be transformed to meet the normal distribution assumption for linear statistical models.

8.1.1 Specific Aim 1

The percent of valid days of FitBit use and length of time will be calculated. We will then examine the percentage of participants who had acceptable adherence as defined as over 5 or more days/week of valid use and 10 or more hours/day length of time.

8.1.2 Specific Aim 2

Given the small sample size power to detect significant associations between physical activity and number of hospital visits will be low. Therefore, these analyses will purely exploratory. We will generate change scores from baseline to 16 weeks for both physical activity variables by subtracting week 16 scores from baseline scores. We will use Poisson regression analyses to examine the associations between changes in physical activity with our dependent variable hospital visit outcomes. Poisson regressions will be fit to account for the fact that our dependent variable (hospital visits) is a count variable and non-normally distributed. All regression models will adjust for baseline level of physical activity. Significance level will be set at 0.05.

8.1.3 Specific Aim 3

All analyses described for aim 3 are also exploratory in nature as the proposed analyses will be underpowered to detect a significant association. Change scores in Quality of life, symptoms of anxiety and depression will be calculated by subtracting week 16 scores from baseline scores. Linear regression analyses will be run examining the associations between change in PA and our dependent variable of change.

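### Aim 3 regresses change in quality of life on change in activity without the baseline quality-of-life score; a baseline-adjusted model should be prespecified beside the change-score model, not in its place

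*Combined protocol and SAP*

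**What the plan says.** Section 8.1.3 defines the outcome as a simple difference: "Change scores in Quality of life, symptoms of anxiety and depression will be calculated by subtracting week 16 scores from baseline scores". The model follows: "Linear regression analyses will be run examining the associations between change in PA and our dependent variable of change". Change in physical activity (PA) is the only predictor named.

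The only baseline adjustment in the statistical section is in 8.1.2, under Aim 2, after the Poisson text: "All regression models will adjust for baseline level of physical activity". The word "All" might be meant to reach Aim 3, but the sentence concerns baseline PA and says nothing of baseline QOL.

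The missing covariate is available. Section 3.1 says "All assessments that include quality of life, exercise behaviors, and self-rated health and mood will be made at baseline and at 16 weeks", and the calendar in section 6.0 marks QOL and the illness perception questionnaire at both visits.

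The study is a single group (3.1) with a planned sample of 20 (3.2). Section 8.1.3 itself calls the Aim 3 analyses exploratory and underpowered.

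**The concern.** A change score contains the baseline score with a negative sign. A woman whose score is low on the day of entry, partly by chance, will tend to score higher at week 16 whatever she does. If such women also change their activity more, or less, than the others, the two changes correlate with no effect of activity. The direction depends on the link. A negative correlation between baseline QOL and PA change produces the positive association that Aim 3a hypothesises. A positive correlation masks a real one.

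Nothing in the design rules this out. PA change is not randomised, and the coaching in section 3.5 sets individual goals and addresses psychosocial barriers, so well-being at entry may well influence how far activity changes. Section 2.1 says that the pilot will supply preliminary data for a larger federal application, so a distorted slope could be carried forward.

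**Working it through.** The documents give no effect size, SD, retest correlation or power figure for Aim 3, so there is no stated figure to reproduce.

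**Inputs from the documents.** n = 20 (3.2). Significance level 0.05, stated under Aim 2 (8.1.2); taken here as two-sided and applied to Aim 3.

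**Assumed inputs.** QOL has SD 1 at each visit and PA change has SD 1. Write r for the QOL correlation between baseline and week 16, and c for the correlation of observed baseline QOL with PA change. Ranges: r = 0.5 to 0.9, c = 0, -0.3 and -0.5. Changes are taken as week 16 minus baseline. The plan's wording reverses the subtraction, but the slope keeps its sign if both changes are computed the same way.

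**Case A: PA change depends on the observed baseline score, no true effect.**
- Expected change-score slope = -c(1 - r). At r = 0.5: 0.3 × 0.5 = 0.15 and 0.5 × 0.5 = 0.25.
- Expected correlation = -c(1 - r)/√(2(1 - r)). At r = 0.5 the denominator is 1, so the values are again 0.15 and 0.25.
- With baseline QOL in the model the expected slope is 0.
- Simulated rejection (60,000 trials per setting):

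| r | c | Change score | With baseline QOL |
|---|---|---|---|
| 0.5 | -0.3 | 9.7% | 5.0% |
| 0.5 | -0.5 | 18.9% | 4.9% |

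At r = 0.7 the change-score model rejects in 7.8% and 12.8%. Repeat simulations gave about 9% to 10% and 18% to 20% for the two change-score figures at r = 0.5.

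- Hidden association: with a true slope of 0.30 and c = +0.5, the change-score slope is 0.30 - 0.5(1 - r), which is 0.05, 0.15 and 0.25 at r = 0.5, 0.7 and 0.9.

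**Case B: PA change unrelated to baseline QOL.** There is no bias and both models reject in about 5%. Adjustment cuts the residual variance by the ratio (1 - r²)/(2(1 - r)) = (1 + r)/2. Allowing for 17 rather than 18 residual degrees of freedom, the SE ratio is √((1 + r)/2 × 18/17):
- r = 0.5: √(0.75 × 1.059) = 0.89, about 11% smaller
- r = 0.7: √(0.85 × 1.059) = 0.95, about 5% smaller
- r = 0.9: √(0.95 × 1.059) = 1.00, no gain

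Simulated mean SEs agree: 0.236 against 0.210 at r = 0.5, and 0.106 against 0.106 at r = 0.9.

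**Case C: PA change depends only on the stable part of QOL, no true effect.**
- Expected change-score slope = 0; simulated rejection about 5%.
- Expected slope with baseline QOL in the model = c(1 - r)/(1 - c²). At r = 0.5: -0.15/0.91 = -0.16 and -0.25/0.75 = -0.33.
- Simulated rejection of the adjusted model at r = 0.5: about 12% and 30%. At r = 0.7: 8.4% and 17.3%.

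**Case D: transient baseline errors in QOL and PA correlated at 0.5, stable parts uncorrelated, no true effect, reliability 0.5.** Slope and rejection:

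| Covariates | Slope | Rejection |
|---|---|---|
| none | +0.25 | 18% |
| baseline PA | +0.17 | 9% |
| baseline QOL | +0.13 | 9% |
| both | +0.09 | 6.5% |

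Both covariates together help most, but some bias remains.

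**The case against.** The strongest objection is that a reader might infer that the change-score model is wrong and should give way to the adjusted one. The documents do not support that. This is a single, non-randomised group, so the choice between the two models rests on an assumption that two visits cannot test. Women who feel worst at entry may do so lastingly rather than on one bad day. That is Case C, where the planned model is sound and the adjusted model produces the false association, at a rate that can exceed the one it removes in Case A. The change-score regression is also the most direct expression of the Aim 3a hypothesis, which relates one increase to another. This objection stands, and it is why the adjusted model belongs beside the planned one.

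Second, the precision gain is not general. It vanishes at r = 0.9, and in Case A with c = -0.5 and r = 0.5 adjustment raises the SE (0.228 to 0.243). This also stands.

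Third, the baseline-PA sentence may already cover Aim 3. That is possible, but it leaves baseline QOL out on any reading.

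Fourth, the primary goal is feasibility and no decision rule depends on the Aim 3 slope. This lowers the severity. It does not make a few sentences of prespecification pointless when the slope is to serve as preliminary data.

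**Conclusion.** The gap is real: the Aim 3 model omits the baseline QOL score although the study collects it. The consequence is conditional. Under a retest correlation of 0.5, n = 20 and no true effect, a link of -0.3 to -0.5 between the observed baseline score and PA change raises false rejection from 5% to about 9% to 19%. With no link the cost is precision alone, from about 11% of the SE at r = 0.5 to nothing at r = 0.9. If the link runs only through stable QOL, the planned model is unbiased and the adjusted one rejects in about 12% to 30%.

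A reader might conclude that the Aim 3 result will be biased, or that adjustment would make it unbiased. Neither follows: the documents give no retest correlation and no information on how activity change relates to entry QOL. What they support is that one model has been chosen without a stated reason where two defensible models can disagree. Severity is low, because the plan declares Aim 3 exploratory and underpowered.

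**What to change.** In section 8.1.3:
- Prespecify, for each quality-of-life measure, a linear model of the week-16 score on change in PA, with the baseline score of that measure and baseline PA as covariates.
- Keep the planned change-score regression and report the two side by side, each with its slope and 95% CI.
- State that an association will be described as supported only if the two slopes agree in direction and rough size. This governs wording and is not a formal test.
- State that the baseline-PA adjustment in 8.1.2 applies to Aim 3.

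Cost: SAP wording, one extra model per measure and no new data. The adjusted model estimates an intercept and three slopes, leaving 20 - 4 = 16 residual degrees of freedom. That is two fewer than the 18 of a model with PA change alone, or one fewer if baseline PA was already intended. Any woman without a week-16 score reduces this further.
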